## 9.2 Pharmacodynamics

Not applicable.

## 10 SAFETY ANALYSES

All safety analysis will be performed for SS-a and SS-s and by treatment group.

### 10.1 Extent of exposure

Extent of exposure is not relevant for the DV0002 substudy. Occurrence of Adverse device effects in this substudy will not be affected by the duration of medication exposure.

### 10.2 Adverse events

All AEs (including serious adverse events [SAEs]) will be reported in a common database for PS0014 and DV0002, but only adverse device effects (ADEs), serious adverse device effects (SADEs), and device deficiencies will be summarized in the DV0002 substudy. Specifically, only those AEs related to the use of the investigational medical devices bimekizumab-SS-

1mL, bimekizumab-AI-1mL, bimekizumab-SS-2 mL or bimekizumab-AI-2 mL (based on the Investigator's judgement) will be assessed. All AEs (including SAEs) which are not assessed to be related to the investigational devices will be summarized separately in the report for the main study PS0014. An exception are AEs that are indicated as injection site reactions during self-injection. These will be listed in DV0002 as well as in PS0014.

### 10.2.1 Adverse device effects

Adverse events are recorded at the AE CRF page at the time when they occur. If an adverse event is related to the device by assessment of the investigator it is counted as an Adverse device event. For DV0002 only ADE will be considered which started during the DV0002 study period. And ADEs started in the 1 ml phase will be included for 1 ml phase analysis, and those started in the 2 ml phase will be included for the 2 ml phase analysis. For 2 ml phase analysis, adverse device effects include those that started on or before the later of the final contact date or (the last injection date + 7 days).

All ADE data will be listed and no statistical testing will be performed. Only treatment-emergent ADEs will be included in the summary tables. Treatment-emergent ADEs (TEADEs) will be defined as events that have a start date on or following the first self-administration of study treatment in DV0002 through the final self-administration of study treatment + 7 days. The device SFU will occur 1 week after the last self-administration.

All ADEs will be coded and classified by system organ class, high level term, and preferred term. Adverse device effects will be summarized by the frequency and percentage of subjects having 1 or more of the events in question. Additional planned summaries include overall ADEs and SADEs. All summaries are presented by PS0014 treatment

- Incidence of TEADEs – Overview
- Incidence of TEADEs by SOC, HLT, and PT
- Incidence of serious TEADEs by SOC, HLT, and PT
- Incidence of TEADEs leading to death
- Incidence of TEADEs leading to discontinuation
- Incidence of non-TEADEs (only listed and not summarized in a table)

For definition of serious, unanticipated and serious unanticipated ADEs see protocol of DV0002.

Adverse device effects which started before DV0002 Week 16 and were ongoing at the data cut off will be included with the status remaining as ongoing. Adverse device effects which were ongoing at DV0002 Week 16 but with an end date before the data cut off will be included with their end date as recorded.

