Additional information (eg, autopsy or laboratory reports) received by the Investigator must be provided within 24 hours. All documents in the local language must be accompanied by a translation in English, or the relevant information included in the same document must be summarized in the Investigator SAE Report Form for Investigational Medical Devices.

The Investigator is specifically requested to collect and report to UCB (or designee) any ADEs or SADEs up to completion of the follow-up visit/telephone call for each subject, and to also inform participating subjects of the need to inform the Investigator of any ADEs or SADEs within this period. Serious AEs that the Investigator thinks may be associated with the device must be reported to UCB regardless of the time between the event and the end of the study.

Upon receipt of the Investigator SAE Report Form for Investigational Medical Devices, UCB will perform an assessment of whether the SADE is anticipated based on the current version of the risk analysis report.

11.1.2.4 Rule for repetition of an adverse device effect, serious adverse device effect, and/or device deficiency

An increase in the intensity of an ADE or SADE should lead to the repetition of the ADE or SADE being reported with:

- The outcome date of the first ADE or SADE that is not related to the natural course of the disease being the same as the start date of the repeated ADE or SADE, and the outcome of “worsening.”
- The ADE or SADE verbatim term being the same for the first and repeated ADE or SADE, so that the repeated ADE or SADE can be easily identified as the worsening of the first one.

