11.1.3 Follow up of adverse device effects and serious adverse device effects

All ADEs and SADEs should be followed until they have resolved, have stable sequelae, the Investigator determines that they are no longer clinically significant, or the subject is lost to follow up.

If an ADE or SADE is ongoing at the end of the study for a subject, follow up should be provided until resolution/stable level of sequelae is achieved, or until the Investigator no longer deems that it is clinically significant, or until the subject is lost to follow up. If no follow up is provided, the Investigator must provide a justification.

Information on SADEs obtained after clinical database lock will be captured through the Patient Safety (PS) database without limitation of time.

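### An adverse device effect that begins in the treatment-emergent window but rises in intensity and becomes serious, fatal or treatment-ending after it closes is missing from the serious, death and discontinuation tables

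*SAP*

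**What the plan says.** Protocol 11.1.2.4 sets the recording rule: "An increase in the intensity of an ADE or SADE should lead to the repetition of the ADE or SADE being reported with" two features. The outcome date of the first record is described as "being the same as the start date of the repeated ADE or SADE", and the first record closes with an outcome of worsening. The link between the two is "The ADE or SADE verbatim term being the same for the first and repeated ADE or SADE".

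SAP 10.2.1 sets the classification rule. TEADEs are "events that have a start date on or following the first self-administration of study treatment in DV0002" and "through the final self-administration of study treatment + 7 days". The same section says "Only treatment-emergent ADEs will be included in the summary tables". The planned outputs are an overview, a table by SOC, HLT and PT, and tables of serious TEADEs, TEADEs leading to death and TEADEs leading to discontinuation. The remaining item is "Incidence of non-TEADEs (only listed and not summarized in a table").

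Protocol 11.1.3 keeps collection open beyond the window: "All ADEs and SADEs should be followed until they have resolved, have stable sequelae" or meet another stated end point. Late worsening would therefore normally be recorded.

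**The concern.** Each rule is reasonable alone. The protocol splits a worsening effect into two dated records, and the SAP then judges treatment-emergence by start date. Neither document says that the second record inherits the status of the first.

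The stage of the effect that matters most for a device, when it becomes serious, is fatal or ends participation, may sit only on the second record. If that record starts after the window, the subject appears in the tables as having a non-serious TEADE and nothing more, although the effect began in the period the tables are meant to cover. Protocol 4.1.1 uses SADEs and ADEs leading to withdrawal to define an unsafe self-injection, so the affected tables describe the events the substudy treats as most important.

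**Working it through.** No sample-size or power figure is involved. The check traces one effect through both rules and does day arithmetic on the nominal schedule.

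**Inputs**
- Self-injection occurs only at DV0002 Baseline and Week 8 (SAP 2.3.2).
- The window ends 7 days after the final self-administration (SAP 10.2.1).
- The substudy lasts at most 16 weeks per subject (SAP 2.3.5).
- Arms are of about 100 subjects (1mL) and about 50 (2mL) (Protocol 5.1.2).

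**Window, with Baseline as Day 1**
- Week 8 = 8 × 7 + 1 = Day 57.
- Window closes on 57 + 7 = Day 64.
- Week 16 = 16 × 7 + 1 = Day 113.
- Exposed period: Days 65 to 113, which is 113 − 64 = 49 days.
- Subject who self-injected only at Baseline: window closes on 1 + 7 = Day 8, so exposure starts on Day 9.

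**Worked example.** A mild ADE starts on Day 60. On Day 70 it rises in intensity and becomes serious.

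| Record | Start | Days after last self-injection | Status | Where it appears |
|---|---|---|---|---|
| First (mild, outcome worsening) | Day 60 | 60 − 57 = 3 | TEADE | Overview; SOC/HLT/PT table |
| Repeated (serious) | Day 70 | 70 − 57 = 13 | non-TEADE | Listings only |

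The subject is counted in the overview and the by-term table, but not in the serious-TEADE table. The death and discontinuation tables behave the same way if the second record carries that outcome or action.

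**Does other text change this?**
- The SAP 10.2.1 paragraph on effects ongoing at data cut-off decides the status and end date shown, not treatment-emergence.
- The 2mL sentence in SAP 10.2.1 (later of final contact or last injection plus 7 days) decides which ADEs are considered for that analysis. It does not alter the TEADE definition.
- The additional summaries of overall ADEs and SADEs in SAP 10.2.1 remain under the TEADE-only restriction.
- The default to treatment-emergent in SAP 4.2 applies to ambiguous or incomplete data. Here both dates are complete.

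**Size per case.** One such subject moves the serious-TEADE entry from 1/50 (2.0%) to 0/50 in a 2mL arm, or from 1/100 (1.0%) to 0/100 in a 1mL arm. No ADE rate is given, so the expected number of cases cannot be computed.

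**The case against.** The strongest objections limit the scope of the point.

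- **Severity alone.** A reader might infer that every summary table loses the severe stage. The documents do not support that. SAP 10.2.1 lists no table by intensity and does not specify the overview rows, so a change to severe but non-serious alters no specified table. This objection stands.
- **Seriousness alone.** Re-entry is triggered by a rise in intensity, and the wording is should, not must. The protocol does not say that an ADE which becomes serious without a rise in intensity gets a second record. If the first record were updated instead, it would keep its in-window start date and be tabulated as serious. This stands, so the point needs both changes.
- **Understated SADE reporting.** A reader might infer that SADEs are hidden or under-reported. They are not. All ADE data are listed, SADEs go to the sponsor within 24 hours (Protocol 11.1.2.1), and SADE information arriving after lock goes to the safety database (Protocol 11.1.3). The primary outcome is taken from the Week 8 self-injection CRF page (SAP 11.1), not from these tables. What is affected is three TEADE tables.
- **Worsening after the substudy.** This might seem to widen the gap, but SAP 10.2.1 separately confines the analysis to ADEs that started during the DV0002 study period. Those records would be out whatever the 7-day limit, so the point stops at the end of the substudy.
- **Record versus event.** The SAP speaks of events, and the shared verbatim term shows that the protocol regards the repeat as a continuation. A programmer could therefore treat the pair as one event. But the protocol gives the repeated ADE its own start date, and the SAP classifies by start date with no linking rule. Applied as written, it yields a non-TEADE, so this objection does not remove the problem.

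The 7-day window itself is not in question. It matches the safety follow-up call one week after the last self-injection.

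**Conclusion.** The point holds in a narrow form. The two rules, applied as written, leave a device effect out of the serious, death or discontinuation TEADE table when all of these are true:

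- it began inside the window;
- it rose in intensity after the window closed but within the substudy;
- the worsened stage is serious, fatal or leads to discontinuation;
- the site followed the re-entry rule and still judged the worsened record device-related.

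The exposed period is nominally Days 65 to 113, or from Day 9 after a single self-injection at Baseline. Actual days shift with the ±7-day visit window. Each case changes a table count by one subject. Such cases are probably few, but the documents give no basis for a number. This is a minor, inexpensive correction to the safety tables. It does not touch the primary result.

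**What to change.** Add to SAP 10.2.1: a record reported under Protocol 11.1.2.4 as the worsening of a treatment-emergent ADE is itself treatment-emergent, whatever its start date. Linked records count as one event per subject, and the worst seriousness, outcome and action taken across them are used in the serious, death and discontinuation tables.

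No new data are needed. The protocol rule already supplies the link: same verbatim term, outcome date of the first record equal to the start date of the second, and an outcome of worsening on the first. The cost is a short SAP addition and a small record-linking step in programming. Serious-TEADE counts may be slightly higher than under the present wording.

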4 STUDY VARIABLES

4.1 Outcome variables

4.1.1 Primary outcome variable

The primary outcome variable is the percentage of subjects able to self-administer safe and effective injections using the bimekizumab-SS-1mL, bimekizumab-AI-1mL, bimekizumab-SS-2mL, or bimekizumab-AI-2mL, 8 weeks after training in self-injection technique. Safe and effective self-injection will be evaluated by the study personnel and is defined as:

- Complete dose delivery: Subject self-injects the complete dose of bimekizumab as confirmed by a visual inspection of the device which shows that the IMP is delivered completely (ie, container is empty), and
- No ADEs that would preclude continued use of the device for self-injection (ie, no SADEs and/or ADEs leading to withdrawal from the DV0002 substudy).

In the DV0002 substudy, for the 1mL devices, the 320mg bimekizumab dose will be administered as two 160mg injections with either 2 bimekizumab-SS-1mL devices or 2 bimekizumab-AI-1mL devices. Each self-injection will be evaluated for safety and effectiveness by study personnel using the above criteria. The endpoint of safe and effective self-injection will be met only if both self-injections are determined to be safe and effective.

For the 2mL devices, the 320mg bimekizumab dose will be administered as 1 injection with either 1 bimekizumab-SS-2mL or 1 bimekizumab-AI-2mL device. Each self-injection will be evaluated for safety and effectiveness by study personnel using the above criteria. The endpoint of safe and effective self-injection will be met if the single self-injection is determined to be safe and effective.

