### **2.3.2 Treatment Period**

During the 16-week Treatment Period of DV0002, subjects will receive either bimekizumab 320mg Q8W or bimekizumab 320mg Q4W, based on their assigned dose at PS0014 Baseline. Baseline for DV0002 and Baseline for PS0014 will occur at the same time for the 1mL device cohort. In the 2mL device cohort, Baseline for DV0002 will occur at the PS0014 Week 24, Week 28, or Week 32 visit for subjects receiving bimekizumab Q4W or the PS0014 Week 24 or Week 32 visit for subjects receiving bimekizumab Q8W.

Eligible subjects (PS0014 entry criteria and DV0002 entry criteria) will be randomly assigned in a 1:1 ratio to perform self-injection using either the bimekizumab-SS-1mL or the bimekizumab-AI-1mL for the 1mL device cohort or using either the bimekizumab-SS-2mL or the bimekizumab-AI-2mL for the 2mL device cohort. Regardless of the assigned dose regimen, subjects will perform self-injection with the assigned device only at DV0002 Baseline and at DV0002 Week 8. For subjects in the bimekizumab 320mg Q4W dosing arm, injections will be administered by study personnel using the investigational device at Week 4 and Week 12; for subjects in both dosing arms, injections will be administered by study personnel using the investigational device at Week 16.

First treatment for the 1ml device cohort in PS0014 will be the timepoint of first bimekizumab injection in DV0002. First treatment in DV0002 will be the timepoint of first self-injection in DV0002.

After Week 16 in the DV0002 substudy, subjects will continue in PS0014.

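### The TEADE window ends 7 days after the last self-injection, so an ADE that starts after Day 8 and leads to withdrawal before Week 8 is listed but cannot enter the ADE tables

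*SAP*

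**What the plan says.** SAP 10.2.1 defines TEADEs as "events that have a start date on or following the first self-administration of study treatment in DV0002" and closes the window "through the final self-administration of study treatment + 7 days". It then restricts the tables: "Only treatment-emergent ADEs will be included in the summary tables". ADEs outside the window go to a listing: "Incidence of non-TEADEs (only listed and not summarized in a table". The tables planned in that section all concern TEADEs: the overview, the system-organ-class breakdown, serious events, deaths, and "Incidence of TEADEs leading to discontinuation".

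SAP 2.3.2 fixes when the device is self-used: "subjects will perform self-injection with the assigned device only at DV0002 Baseline and at DV0002 Week 8".

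For the 2mL cohort, SAP 10.2.1 also says which ADEs belong to the analysis at all: those starting by "the later of the final contact date or (the last injection date + 7 days"). That sentence does not amend the TEADE definition or the rule on what is tabulated. The 1mL cohort has no counterpart.

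Protocol 14.5 likewise admits only treatment-emergent ADEs to the tables but gives no window. Protocol 11.1.2.3 has ADEs collected until the follow-up call is done. Protocol 6.3 places that call, for a withdrawn subject, one week after the last DV0002 dosing visit, whoever gave the dose.

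**The concern.** The end of the window depends on something that happens after the event, namely whether the subject self-injects at Week 8. Two subjects with the same ADE on Day 20 are treated differently: it is tabulated in the one who self-injects at Week 8 and only listed in the one who withdraws first. If the ADE caused the withdrawal, it is left out of the tables as a consequence of its own outcome. The discontinuation table is the most exposed, because an event that starts after Day 8 and ends participation before Week 8 cannot appear there by construction. A serious ADE in the same position would also miss the serious table.

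This matters because the protocol treats such events as central to safe use. Its definition of a safe self-injection requires "no SADEs and/or ADEs leading to withdrawal from the DV0002 substudy". A descriptive table that is closed to some of those events can only err downward.

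**Working it through.** **Inputs**
- Day numbering: first dose is Day 1 (SAP 3.4).
- Self-injections: Baseline and Week 8 only (SAP 2.3.2).
- Dosing window: ±7 days (Protocol Tables 5-3 and 5-5, footnotes).
- Planned arm sizes: about 100 per 1mL device and 50 per 2mL device (SAP 2.3.6).
- Number of affected events: not in the documents. Assumed here at 1, with 1 to 3 shown as a range.

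**The plan's own figure.** Week 8 is Day 1 + 56 = 57. Seven days later is Day 64. Week 9 is Day 1 + 63 = 64. The window end therefore coincides with the Week 9 follow-up call (SAP 2.3.3) for a subject who self-injects twice.

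**Window by subject type**
- Self-injects at Week 8: Day 1 to 57 + 7 = Day 64.
- No Week 8 self-injection: Day 1 to 1 + 7 = Day 8.

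**Uncovered days before Week 8.** Days 9 to 56: 56 − 8 = 48 days. With the dosing window:
- Week 8 injection on Day 50: 49 − 8 = 41 days; window ends on Day 57.
- Week 8 injection on Day 64: 63 − 8 = 55 days; window ends on Day 71.

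**Collection against tabulation.** A Q4W subject who withdraws after the study-personnel dose at Week 4 (Day 29) has the follow-up call at about 29 + 7 = Day 36. ADEs are collected to about Day 36 but tabulated only to Day 8.

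**Scale.** The exact (Clopper-Pearson) 90% upper limit is the 0.95 quantile of Beta(x + 1, n − x). For x = 0 it reduces to 1 − 0.05^(1/n).

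| Events | n = 50: rate (90% CI) | n = 100: rate (90% CI) |
|---|---|---|
| 0 (as tabulated) | 0% (0 to 5.8%) | 0% (0 to 3.0%) |
| 1 | 2% (0.1 to 9.1%) | 1% (0.05 to 4.7%) |
| 2 | 4% (0.7 to 12.1%) | 2% (0.4 to 6.2%) |
| 3 | 6% (1.7 to 14.8%) | 3% (0.8 to 7.6%) |

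The top row is what the TEADE tables would show if all such events fell in the gap and no others occurred. The intervals serve only to show scale; the study is descriptive.

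**The case against.** The case for leaving the rule alone has substance.

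- **A post-injection window is deliberate.** Seven days matches the device follow-up call and the rule for injection site reactions (SAP 10.2.2). An ADE has to arise from the instructions, the operation or malfunction of the device, or use error or misuse (SAP 2.2.3.3), and SAP 10.1 states that duration of medication exposure does not affect occurrence. Onset more than a week after the only self-injection, attributed to the device and severe enough to cause withdrawal, should be rare. This stands, and it means that 48 days measures calendar time, not a share of the risk.
- **Nothing is lost from the record.** All ADEs are listed, and SAP 5.1 tabulates discontinuations with reasons by treatment and device group. This also stands. A reader might infer that the event disappears from the report; it does not.
- **The endpoints are untouched.** A reader might infer that the window biases the primary result, since ADEs leading to withdrawal are part of its safety criterion. SAP 11.1 and 11.2 take both percentages from the self-injection CRF pages, so the window enters neither.
- **Staying in is not the dividing line.** A subject who remains in DV0002 but is injected by someone else at Week 8 also has a window ending on Day 8. Conversely, an ADE that starts by Day 8 and leads to a later withdrawal is tabulated.
- **A simple extension to final contact would overshoot.** For most completers the last DV0002 contact is Week 16, Day 1 + 112 = 113. That would add 113 − 64 = 49 days in which no self-injection occurs. Nor is it the 2mL end point already in the SAP, which refers to the last injection and not the last self-injection.

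These points limit the weight of the concern and shape the remedy. None supplies a reason for tabulating an ADE starting on Day 20 in one subject and not in another.

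**Conclusion.** The point holds for both cohorts on the current SAP text, as a narrow gap in the descriptive safety tables. An ADE starting after Day 8 in a subject with no Week 8 self-injection is not a TEADE; if it leads to withdrawal before Week 8, it is closed to the discontinuation table and, where serious, to the serious table. Those rates can be biased downward, never upward.

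The likely number of affected events is near zero, but the documents give no rate. Under the assumption of one event, a 2mL arm would show 0/50 in place of 1/50, and a 1mL arm 0/100 in place of 1/100. The conclusion assumes that the 2mL inclusion sentence does not override the TEADE definition. That sentence may have been meant to widen the tables, but it does not say so. It deserves correction because the omission selects on withdrawal and is cheap to remove, not because a large effect is expected.

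**What to change.** In SAP 10.2.1, for both cohorts:

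1. Keep the present end of window, seven days after the last self-injection, for subjects who self-inject at Week 8.
2. For subjects with no Week 8 self-injection, end the window at the later of (a) seven days after the first self-injection and (b) the earlier of the final DV0002 contact or withdrawal date and Day 64 (Week 9).
3. Add a table of all ADEs that start on or after the first self-injection and lead to discontinuation of DV0002, whatever their onset relative to the window.
4. Reconcile the 2mL inclusion sentence, which counts from the last injection, with the TEADE sentence, which counts from the last self-injection, and state whether the former affects the tables.
5. Show days since last self-injection in the ADE listing, so that late events can be judged.

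The cost is a few sentences of SAP text and a programming change, with no new data collection. The downside is that a few late-onset events attributed to the device will enter the tables. Capping the window at Day 64 keeps completers' TEADE windows as they are.
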